10.7.6 Videography

~~Videography, using standardized technology and equipment, will be used to evaluate patient response. An approximate 20-minute video will be obtained at each protocol specified time point and the patient's head/face area will be evaluated for ptosis, extra-ocular movements, facial strength (i.e. smile, eye closure, puffing cheeks), and speech, as age permits.~~

On Page 54, under 11.1 Adverse Events, changed text

The study period during which all non-serious AEs will be reported begins after informed consent is obtained and the first administration of study drug through the last visit (Study Day **36** **29**) or at the early termination visit.

On Page 61, under 13.1 Screening Visit, deleted and added text

- **~~Patient video;~~**
- Stimulated single fiber EMG (*optional*);

- CGI-S;
- Slurp test (*optional*);
- Assessment of **AEs/SAEs**; and
- Assessment of concomitant medications.

On Page 62, under 13.2 Open-label Run-in, deleted text

Improvement of at least 20% in MFM 20 or 32 is not a requirement for these participants. ~~They must have not been previously assessed for improvement in subject global impression (SGI) and motor function measure (MFM 20 or 32) scores within 3 months prior to participating in this study to avoid possible testing bias.~~

On Page 62, under 13.2 Open-label Run-in, deleted and added text

- **Patient video;**
- CGI-S;
- CGI-I; and
- Slurp test (*optional*).

Assessment	Start Time After Dose* (\pm 10 minutes unless otherwise specified)
SGI	40 minutes
MFM 20 or 32	after SGI
Patient video	after MFM
Slurp test, CGI-S and CGI-I	At end of assessments

*Administration of medication represents Time 0 (minutes)

~~At the end of the MFM testing, the patient's face will be evaluated for ptosis, extra-ocular movements, facial strength (i.e. smile, eye closure, puffing cheeks), and speech, as age permits.~~

The site pharmacy will dispense bottles containing **blinded** amifampridine phosphate or placebo tablets, depending on the patient's Treatment Sequence assignment, for daily outpatient administration for 7 days (Days 1-7). Administration of blinded study medication

will begin with ~~the first morning dose on Day 1 of Period 1 the next scheduled dose following the Day 0 baseline assessment on open-label medication. (see Section 13.3).~~

On Page 63, under 13.3 Period 1, deleted text

~~On Day 1, patients will begin administration of randomized study medication (amifampridine phosphate or placebo tablets) with the first morning dose.~~

Administration will be continued on an outpatient basis for a total of 7 days (Days 1-7).

On Page 64, under 13.3 Period 1, deleted and added text

- o ~~Patient video;~~
- o CGI-S;
- o CGI-I; and
- o Slurp test (*optional*).

Assessment	Start Time After Dose* (\pm 10 minutes unless otherwise specified)
SGI	40 minutes
MFM 20 or 32	after SGI
Patient video	after MFM
Stimulated Single fiber EMG	after video MFM
Slurp test, CGI-S and CGI-I	At end of assessments

*Administration of medication represents Time 0 (minutes)

~~At the end of the MFM testing, the patient's face will be evaluated for ptosis, extra-ocular movements, facial strength (i.e. smile, eye closure, puffing cheeks), and speech, as age permits.~~ If the stimulated single fiber EMG (optional assessment) is not to be performed, then the slurp test (also optional), CGI-S and CGI-I assessments should be done following completion of the ~~video of the patient's head area~~~~MFM~~.

Open-label amifampridine phosphate will be dispensed at the Day 8 visit for administration during the stabilization period, starting ~~on Day 9 with the next scheduled dose after Day 8 assessments (see Section 13.4).~~

On Page 64 and 65, under 13.4 Re-stabilization Period, deleted and added

- o ~~Patient video;~~

- CGI-S;
- CGI-I; and
- Slurp test (*optional*).

Assessment	Start Time After Dose* (\pm 10 minutes unless otherwise specified)
SGI	40 minutes
MFM 20 or 32	after SGI
Patient video	after MFM
Slurp test, CGI-S and CGI-I	At end of assessments

* Administration of medication represents Time 0 (minutes)

~~At the end of the MFM testing, the patient's face will be evaluated for ptosis, extra-ocular movements, facial strength (i.e. smile, eye closure, puffing cheeks), and speech, as age permits~~ The slurp test (optional), CGI-S and CGI-I assessments should be done following completion of the ~~video of the patient's face~~ MFM.

The site will dispense bottles containing amifampridine phosphate or placebo tablets, depending on the patient's Treatment Sequence assignment, for Period 2 (Days 22-28). Administration of blinded study medication will begin with the *next scheduled dose after Day 21 assessments are completed*~~first morning dose on Day 22 of Period 2~~ (see *Section 13.5*).

On Page 65, under 13.5 Period 2, deleted and added text

~~On Day 22, p~~Patients will ~~begin administration with the first morning dose of the randomized~~ the blinded study medication they did not receive in Period 1. Administration will be continued on an outpatient basis for a total of 7 days (Days 22-28).

Patients will report to the study site on Day 29 (+1 day) and receive a dose of the same study medication they received for the previous 7 days, under the supervision of the study personnel, in order to time the following assessments/procedures in relation to the medication dose.

- Assessment of AEs/SAEs;
- ~~Abbreviated~~ **Complete** physical exam with weight;

- Vital signs (seated position), including SBP, DBP, heart rate, respiration, and body temperature;
- Standard resting 12-lead ECG;
- Clinical laboratory tests;
- Urine pregnancy test in females of childbearing potential only;
- Concomitant medications;
- IP accountability;
- Efficacy assessments, including:
 - o MFM 20 or 32;
 - o SGI (patient/parent/guardian/caregiver);
 - o Stimulated single fiber EMG (*optional*);
 - o **Patient video;**
 - o CGI-S;
 - o CGI-I; and
 - o Slurp test (*optional*).

Assessment	Start Time After Dose* (± 10 minutes unless otherwise specified)
SGI	40 minutes
MFM 20 or 32	after SGI
Patient video	after MFM
Stimulated Single fiber EMG	after videoMFM
Slurp test, CGI-S and CGI-I	At end of assessments

*Administration of medication represents Time 0 (minutes)

~~At the end of the MFM testing, the patient's face will be evaluated for ptosis, extra-ocular movements, facial strength (i.e. smile, eye closure, puffing cheeks), and speech, as age permits~~ If the stimulated single fiber EMG (optional assessment) is not to be performed, then the slurp test (also optional), CGI-S and CGI-I assessments should be done following completion of the ~~video-MFM of the patient's head area~~.

 Catalyst pharmaceuticals	CMS-001 Version Amendment 5	Page 121
--	--------------------------------	----------

After completion of the above procedures/assessments, patients will be ~~restored to open-label amifampridine phosphate at the same dose and frequency as established in the run-in phase of the study and they will be~~ eligible for an expanded access program.

On Page 66, under 13.5 Period 2, deleted section

13.6 Safety Follow Up

~~Patients taking open-label amifampridine phosphate, following Study Day 29 visit, will return to the study site on Day 36 (+2 days) for a final safety assessment, including:~~

- ~~Assessment of AEs/SAEs;~~
- ~~Complete physical exam with weight;~~
- ~~Vital signs (seated position), including SBP, DBP, heart rate, respiration, and body temperature;~~
- ~~Standard resting 12-lead ECG;~~
- ~~Urine pregnancy test in females of childbearing potential only; and~~
- ~~Concomitant medications;~~
- ~~IP accountability.~~

On Page 66, under 13.6 Early Discontinuation Visit, changed text

13.7 13.6 Early Discontinuation Visit

On Page 66 and 67 under 13.6 Early Discontinuation Visit, deleted and added text

- o Stimulated Single fiber EMG (*optional*);
- o **Patient video;**
- o CGI-S;
- o CGI-I; and
- o Slurp test (*optional*).

 Catalyst <small>pharmaceuticals</small>	CMS-001 Version Amendment 5	Page 122
---	--------------------------------	----------

Appendix 10: Protocol Amendment 5

PURPOSE: The purpose of this amendment is as follows:

To formally remove the videotaping of patients from the protocol, clarify the start and stop times of Periods 1 and 2, blinded medication dosing, and remove the Day 36 visit. The patient is either on a stable dose of amifampridine phosphate or has been titrated over a period of 4 weeks. Also, the patient is observed on open label medication for 2 weeks during the restabilization period. Therefore, the Day 36 visit on open label medication adds no new information to the efficacy or safety profile of amifampridine phosphate and the patient may go directly into the expanded access program.

Risk: these administrative changes provide clarity, adding no additional risk to the patient.

MODIFICATIONS TO PROTOCOL:

- **Bold and underlined text:** Changed Text
- **Bold and strike through text:** Deleted Text
- ***Bold and italicized text:*** Added Text

On Page 1, under Clinical Study Protocol, added text

Date of Amendment 5: 26 June 2017

On Page 32, under 8.4.4 Safety of Amifampridine and Amifampridine Phosphate, added text

Based upon the previous clinical studies involving the use of amifampridine in the treatment of Lambert-Eaton myasthenic syndrome (LEMS), there have been reports of provocation of bronchial asthma, respiratory failure, or respiratory disorder. These events are also part of CMS symptoms; however, the risk may be more likely when the patient has asthma or respiratory disorder as a comorbidity with CMS.

On Page 33, under 8.5 Overall Risks and Benefits, added and deleted text

Risks of study involvement have been minimized by:

1. *Patients entering the study may already be on some formulation of 3,4-diaminopyridine and have demonstrated tolerability or;*
2. *Patients naïve to the medication are titrated to a tolerable and effective dose with open-label medication, under the observation of the Investigator. Thus, the development of adverse events or lack of efficacy is monitored by the Investigator during the step-wise*

 Catalyst pharmaceuticals	CMS-001 Version Amendment 5	Page 123
--	--------------------------------	----------

titration and study medication dose can be reduced or discontinued at any point in the titration for either safety or lack of efficacy.

The pharmacokinetic half-life of amifampridine phosphate is short (1.8 hours), therefore discontinuation of medication will quickly terminate the effects, and mitigate adverse reactions.

This is a withdrawal study design looking at patient worsening on placebo; which is possible due to the short half-life of amifampridine phosphate. Therefore, patients must demonstrate a level of efficacy during the open-label titration period. This further reduces patient risk, by not continuing an experimental medication in patients who fail to demonstrate a benefit.

During the placebo withdrawal period, patients who deteriorate to a point that the Investigator assess to be lower than their baseline, open-label amifampridine phosphate is provided as to rescue the patient.

Refer to the Firdapse Investigator Brochure (February, 2015) for further **discussion information** on benefit/risk of amifampridine.

On Page 51, under Table 5. Medications Prohibited During Study added and deleted text

The following medicinal products should be used with caution in patients taking amifampridine phosphate:

Medicinal products known to cause cardiac QT prolongation

Medicinal products known to lower epileptic threshold

Medicinal products with atropinic effects

The concomitant use of amifampridine phosphate and medicinal products with atropinic effects may reduce the effect of both active substances and should be taken into consideration. Medicinal products with atropinic effects include tricyclic anti-depressants, most H1 atropinic anti-histamines, anticholinergic, anti-Parkinson medicinal products, atropinic antispasmodics, disopyramide, phenothiazine neuroleptics and clozapine.

Medicinal products with cholinergic effects

The concomitant use of amifampridine phosphate and medicinal products with cholinergic effects (e.g. direct or indirect cholinesterase inhibitors) may lead to an increased effect of both products and should be taken into consideration.

Non-depolarizing muscle relaxant acting medicinal products

 Catalyst pharmaceuticals	CMS-001 Version Amendment 5	Page 124
---	--------------------------------	----------

The concomitant use of amifampridine phosphate and medicinal products with non-depolarizing muscle relaxant effects (e.g. mivacurium, pipercurium) may lead to a decreased effect of both products and should be taken into consideration.

Depolarizing muscle relaxant acting medicinal products

The concomitant use of amifampridine phosphate and medicinal products with depolarizing muscle relaxant effects (e.g. suxamethonium) may lead to a decreased effect of both products and should be taken into consideration.

~~Concomitant use of amifampridine phosphate with medicinal products with atropinie effects may reduce the effect of amifampridine phosphate, which should be taken into consideration.~~

1.0 Synopsis of Study Design Procedure

This statistical analysis is based on and consistent with the CMS-001 Protocol Amendment 5, dated June 26, 2017.

1.1 Design and Treatment

This randomized (1:1), double-blind, placebo-controlled, outpatient two-period, two-treatment crossover study is designed to evaluate the efficacy and safety of amifampridine phosphate in patients diagnosed with certain genetic subtypes of CMS and demonstrated open label (amifampridine phosphate) or history of sustained amifampridine benefit from treatment. The primary objectives of this study are to:

- Characterize the overall safety and tolerability of amifampridine phosphate compared with placebo in individuals with CMS; and,
- Assess the clinical efficacy of amifampridine phosphate compared with placebo in individuals with CMS, based on change in Subject Global Impression (SGI) and Motor Function Measure (MFM 20 or 32) scores.

CMS-001 is a randomized double-blind, placebo controlled, two-period two-treatment crossover study designed to evaluate the efficacy and safety of amifampridine phosphate in children (2-16 years of age) and adults (17 years of age or more) diagnosed with CMS. Patients were randomized (1:1) to one of two sequences:

PA: Placebo – Amifampridine, or
AP: Amifampridine – Placebo.

The study was planned to include up to 23 male and female subjects. The planned duration for each patient is approximately 56 days, excluding the screening period. The screening period may last up to 14 days.

1.2 Study Procedures

Amifampridine phosphate oral dosing using 10 mg tablets starts on Day 1 of the open-label run-in and patients were titrated upward every 3 to 4 days, per guidelines in the protocol and at the discretion of the investigator, for up to 4 weeks, with 1 week of stable dose and frequency at the end of the run-in period before being randomized. Dosing and/or dosing frequency was increased or decreased by the investigator during the run-in phase prior to the last week of stable dosing. Per the protocol, randomization could only occur after the patient has been on a stable dose and dosing frequency for at least 7 days.

At the end of their Period 1 randomization treatment, patients will return to open-label amifampridine phosphate for 14 days between Periods 1 and 2 at the same dose and

dosing frequency established in the run-in phase. No dose adjustments were allowed during this re-stabilization period.

After completing Period 2, (the completion point for this trial) patients were eligible for an open-label amifampridine phosphate treatment protocol (CMS-002).

1.3 Sample Size

The primary analysis variable is the SGI Change from Baseline (CFB). It will be analyzed using the standard analysis for a two-by-two crossover design. The sample size required to control the power depends on the ratio of the between-treatment difference and the standard deviation of the difference (that is, the effect size). Assuming an effect size of 0.5, 23 patients per sequence will ensure power of 90% for the 2-sided test at the 0.05 level.

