10 INVESTIGATIONAL PLAN

10.1 Overall Study Design and Plan

This is a randomized (1:1), double-blind, placebo-controlled, outpatient two-period two-treatment crossover study designed to evaluate the efficacy and safety of amifampridine phosphate in patients (2 years of age and above) diagnosed with CMS. The study is planned to be conducted at up to 5 sites in the United States and 2 sites in Canada, to include approximately 23 male and female patients. The planned duration of participation for each patient is approximately 56 days excluding the screening period, which can last up to 14 days.

All patients (parent or legal guardian) who sign an informed consent will be screened for eligibility to participate in the study, including: inclusion and exclusion criteria; medical and medication history; complete physical exam; standard 12-lead ECG; laboratory testing; serum pregnancy testing (females of childbearing potential only; result must be negative to

proceed into the run-in period with open-label IP administration); and CMS genetic testing (if not previously done or available).

Those patients successfully completing initial screening will have procedures/assessments (see [Table 3](#)) conducted on Day 1 of the run-in period. Those not previously on 3,4-DAP or amifampridine phosphate will then embark on an open label up-titration of amifampridine phosphate dose based upon clinical benefit (assessed at clinic visit and telephone solicitation) for up to 4 weeks during run-in period, until stable dose and frequency of amifampridine phosphate is achieved for 7 days. If these patients have demonstrable increase of MFM 20 or MFM 32 scores of >20% during this period of open label uptitration of dose, patients will then be randomized to a Treatment Sequence on last day of open-label run-in period (Day 0).

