10.2.4 Patient Identification and Randomization

Each patient will be assigned a unique patient identification number. Upon signing of the ICF, subjects will be assigned an ID composed of a two digit site number and a two digit subject number (e.g. site 1 subject 1 would be assigned 01-01). Screen failures that are allowed to be re-screend will keep the same site assigned ID. There are no plans to replace subjects that drop out of the study.

 Catalyst pharmaceuticals	CMS-001 Version Amendment 5	Page 44
--	--------------------------------	---------

Randomization will be across sites to maintain the 1:1 ratio of drug:placebo assignment. The assignments to treatment (amifampridine phosphate or placebo) will be based on a computer-generated randomization code. A central point of contact will be provided to the site pharmacist to obtain the treatment sequence for the subject to be enrolled in Period 1 on the last day of the run-in period (Day 0).

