15 STATISTICAL METHODS AND DETERMINATION OF SAMPLE SIZE

15.1 Determination of Sample Size

Assuming a standardized between-treatment difference of 0.5, 23 patients per sequence will ensure power of 90% for the 2-sided test at the 0.05 level using the standard 2-by-2 crossover analysis.

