2.0 Data Analysis Considerations

2.1 Types of Analyses

The term summary statistics for quantitative data refers to the following list of statistics unless otherwise specified: n (number of non-missing observations), mean, standard deviation, minimum, median, and maximum. Categorical variables will be summarized with frequency counts and percentage of the relevant group. Summary statistics will be summarized by treatment sequence and study period. Unless otherwise stated, all hypotheses will be tested at a two-sided $\alpha = 0.05$ significance level

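### The 90% power claim is for 46 patients (23 per sequence), but the plan enrols about 23 in total, which gives about 63% power

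*SAP*

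**What the plan says.** SAP section 1.3 names change from baseline in SGI as the primary variable, to be analysed by the standard two-by-two crossover method. It defines the effect size as the between-treatment difference divided by the standard deviation of that difference, and then states: "Assuming an effect size of 0.5, 23 patients per sequence will ensure power of 90% for the 2-sided test at the 0.05 level". Protocol section 15.1 makes the same claim: "Assuming a standardized between-treatment difference of 0.5, 23 patients per sequence will ensure power of 90% for the 2-sided test at the 0.05 level". The protocol synopsis repeats it.

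The planned enrolment is stated separately:

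- SAP 1.1: "The study was planned to include up to 23 male and female subjects". The same section describes 1:1 randomisation to two sequences.
- Protocol 10.1: "to include approximately 23 male and female patients".
- The protocol synopsis gives up to 23 patients under the study design and approximately 23 under the number of patients planned.

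On losses, protocol 10.2.4 says: "There are no plans to replace subjects that drop out of the study". SAP 2.3 specifies complete-case analysis without imputation. Neither document states a dropout allowance.

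**The concern.** The same number, 23, is a per-sequence count in the power statement and a total in the enrolment plan. Both cannot be right in a two-sequence trial. No current text plans 46 patients, and none gives a power for 23.

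What is at stake is how the result is read. Someone who sees a non-significant SGI result from a trial described as 90% powered will take it as fairly strong evidence against the assumed effect. If the true power is much lower, that inference is unsafe. The sentence is in the sample-size justification of both governing documents, so it will probably be carried into the study report.

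**Working it through.** **Inputs**

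- Effect size d = difference / SD of the within-patient difference = 0.5 (SAP 1.3).
- Two-sided test at 0.05 (SAP 1.3 and 2.1; protocol 15.1).
- Two sequences, 1:1 (SAP 1.1).
- Sizes to compare: 23 + 23 (power statement) and 12 + 11 (enrolment of 23).

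**Formula**

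In the standard 2-by-2 crossover analysis the treatment effect is half the difference between sequences in the mean period difference. In units of the SD of the within-patient difference:

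- SE = ½ × √(1/n₁ + 1/n₂)
- noncentrality = d / SE
- df = n₁ + n₂ − 2
- power = probability that a noncentral t with this df and noncentrality falls beyond ± t(0.975, df)

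**Step 1: reproduce the plan's figure (23 + 23)**

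- SE = ½ × √(2/23) = 0.1474
- noncentrality = 0.5 / 0.1474 = 3.391
- df = 44, critical value 2.015
- power = 91.2%

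With 22 + 22 the power is 89.97%, just short of 90%. So 23 per sequence is the smallest equal allocation that reaches the target. The wording *per sequence* agrees with the arithmetic.

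**Step 2: the planned enrolment (12 + 11)**

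- SE = ½ × √(1/12 + 1/11) = 0.2087
- noncentrality = 0.5 / 0.2087 = 2.396
- df = 21, critical value 2.080
- power = 62.7%, so the chance of missing the assumed effect is 100 − 62.7 = 37.3%

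**Step 3: other sizes and effects**

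| Patients analysed | Power at d = 0.5 |
|---|---|
| 46 (23 + 23) | 91.2% |
| 44 (22 + 22) | 89.97% |
| 23 (12 + 11) | 62.7% |
| 20 (10 + 10) | 56.2% |
| 18 (9 + 9) | 51.3% |

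The rows for 20 and 18 only illustrate losses, since the documents give no dropout rate. With 12 + 11, 80% power needs d = 0.61 and 90% needs d = 0.71. At d = 0.5, 80% power needs 34 patients in total.

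**Step 4: could another reading rescue 23 in total?**

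- If 0.5 were in units of the within-patient SD (the SD of the difference being √2 times larger), then d = 0.5/√2 = 0.354. Power would be 65.0% with 46 patients and 36.6% with 23. The stated 90% would then fail even at 46.
- A one-sided 0.05 test with 23 patients gives 74.9%, and both documents specify two-sided.
- 23 patients come close to 90% (89.8%) only if d is 0.5 × √2 = 0.71, which contradicts the SAP's stated value and definition.

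**Step 5: the rank test**

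SAP 4.2.1 applies a Mann-Whitney-Wilcoxon test to the period differences. Simulated with normal data, d = 0.5 and 12 + 11, its power is about 58%. The large-sample efficiency of 3/π gives about 61%. Ties on the 7-point SGI are not modelled in either figure.

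**The case against.** The mismatch itself is hard to dispute, but there are fair points around it.

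- **The effect of 0.5 is not justified in either document, and the true effect may be larger.** The only SGI data given are from the LEMS trial LMS-002 (protocol 8.4.3): a treatment difference of 1.8 and an SD of 2.3 for the change after switching to placebo. Suppose, as an assumption, that 2.3 is the SD of change in each period. Then d = 1.8 / (2.3 × √(2(1 − r))), where r is the within-patient correlation. This is 0.55, 0.64 and 0.78 for r = 0, 0.25 and 0.5, with power at 12 + 11 of about 72%, 83% and 95%. This stands as a reason not to call 63% the trial's true power. It does not rescue the sentence, which is tied to 0.5. The data also come from another disease and a parallel-group design.
- **The documents do not show which number is the slip.** Also true. The arithmetic favours *per sequence* as the correct output of the calculation, but it cannot show what the sponsor intended. Either way the power sentence and the enrolment figure cannot both stand.
- **A t-test power is not the power of every analysis in SAP 4.2.1.** That section specifies rank tests and a mixed model on raw scores. The corrected figure should therefore name its test. The documents size the trial on the standard crossover analysis, so 63% is the like-for-like replacement, and the rank test is somewhat weaker.
- **The correction changes no estimate, test or type I error, and the SAP already speaks of enrolment in the past tense.** True, but the claim governs how a null result is interpreted. Rarity can justify a small trial, but not a power figure that belongs to one twice the size.

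**Conclusion.** The concern holds. Both documents claim 90% power for a design of 46 patients and plan about 23. At the stated effect of 0.5, with the SAP's own definition and a two-sided 0.05 test, the planned trial has about 63% power, roughly 28 percentage points below the 91.2% that 23 per sequence would give (91.2 − 62.7 = 28.5).

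The figure assumes approximately normal period differences, a 12/11 split and every patient completing both periods. Losses or use of the rank test lower it, and a true effect above 0.5 raises it. The sentence is wrong as written and must be corrected.

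**What to change.** Replace the power sentence in the protocol synopsis, protocol 15.1 and SAP 1.3 with wording such as:

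*With about 23 randomised patients (11 to 12 per sequence), the standard 2-by-2 crossover t-test at two-sided 0.05 has about 63% power for a standardised difference of 0.5 (difference divided by the SD of the within-patient difference), 80% for 0.61 and 90% for 0.71. The rank test has slightly lower power (about 58% at 0.5, by simulation with normal data). Dropouts are not replaced, so power falls with any loss.*

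If the sponsor intended a different effect size or definition, it should be stated and justified in the same place.

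The cost is wording, and a less favourable stated figure. No extra enrolment and no change to design, endpoint or analysis is needed. Changing the protocol text means an amendment. If one is not practical, correct SAP 1.3 and record there that the figure differs from the protocol, as protocol 15.6 provides for.
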